2.4. Week 52 / Early End of Study Visit (Visit 11 –Week 52)

- Contact IXRS
- Physical examination (PE).
- Vital signs, including systolic and diastolic blood pressure, pulse, respiratory rate, and body temperature.

- 12-lead electrocardiogram (ECG).
- ECOG performance status assessment
- Concomitant medications.
- Adverse events.
- Laboratory testing including hematology, blood chemistry, urinalysis, serum β 2 microglobulin, and lactate dehydrogenase (LDH).
- HBV DNA testing in patients with occult or prior hepatitis B infection (defined as positive total HBcAb and negative HBsAg) at screening.
- Serum pregnancy test (human chorionic gonadotrophin; hCG) for women of childbearing potential.
- PD (CD19+ B-cell count) sampling.
- IgG and IgM sampling.
- Immunogenicity sampling.

2.5. Early Treatment Discontinuation Visit

At an Early Treatment Discontinuation visit, the same assessments should be conducted as at Week 28 / Early End of Study, with the following additional assessments:

- Ann Arbor staging – only for patients who need to start a new treatment.
- Bone marrow biopsy – only for patients with positive findings at screening, to confirm CR based on investigator's review of CT scan
- CT scan (MRI scan where contrast is contraindicated) – only for patients who discontinue study drug early for any reason and need to start a new treatment before the Week 28 visit.

2.6. Unscheduled Visit

- Unscheduled visits should be scheduled as per Investigator discretion. Tests will be selected as per Investigator's discretion.

2.7. Phone Visit

As a measure to minimize lost to follow-up, a phone visit can be tried.

- ECOG performance status assessment
- Concomitant medications.
- Adverse events.

APPENDIX 11: DEFINITION OF PROGRESSION THAT WARRANTS INITIATION OF TREATMENT CHEMOTHERAPY/RADIOTHERAPY.

Modified based on the publication:

Ardeshta KM1, Qian W, Smith P, Braganca N, Lowry L, Patrick P, Warden J, Stevens L, Pocock CF, Miall F, Cunningham D, Davies J, Jack A, Stephens R, Walewski J, Ferhanoglu B, Bradstock K, Linch DC. Rituximab versus a watch-and-wait approach in patients with advanced-stage, asymptomatic, non-bulky follicular lymphoma: an open-label randomised phase 3 trial. *Lancet Oncol.* 2014; 15: 424-35.

It is recognized that it is difficult to clearly define when disease progression is sufficient to warrant the initiation of chemotherapy or radiotherapy. The following is suggested guidance:

1. Development of symptomatic enlarged lymph nodes or spleen.
2. The development of B symptoms or severe pruritus.
3. Lymphomatous mass >7cm provided it has increased in size by at least 25%.
4. More than 3 sites with diameter >5cm.
5. The development of significant serous effusions, clinically or on CT (small, clinically non-evident effusions on CT scan are not an indication to start chemotherapy).
6. Hemoglobin <100g/L (10g/dL), absolute neutrophil count <1.5x10⁹/L (1,500/mm³), platelet <100x 10⁹/L (100,000/mm³) not attributable to other causes. If asymptomatic this should persist for >1 month.
7. Critical or near critical organ involvement or organ compression, e.g. ureteric obstruction, epidural compression.
8. A rising LDH is not in itself an indication to initiate therapy but may trigger further investigations.

## Modification History

Unique Identifier for this Version	Date of the Document Version	Author	Significant Changes from Previous Authorized Version
Final V1.0	10Sep2019		Not Applicable – First Version

---

Document:

Author:

Version Number:

Version Date:

Final v1.0

10Sep2019

Template No: CS\_TP\_BS016 Revision 4

Effective Date: 01Apr2016

Reference: CS\_WI\_BS005

## LIST OF ABBREVIATIONS AND DEFINITIONS OF TERMS

Abbreviation	Definition
ADA	Anti-drug antibody
AE	adverse event
AESI	adverse event of special interest
ATC	anatomical therapeutic chemical
AUC	area under the concentration-time curve
AUC 0-inf	area under the concentration-time curve from time 0 to infinity
AUC 0-168	truncated AUC over the dosing interval
AUC 0-W1	area under the curve from time 0 to Week 1
AUC WX-WY	area under the curve from Week X to Week Y
AUEC	Area under the PD variable-time effect curve
AUEC 0-168	truncated AUEC over the dosing interval
AUEC 0-WX	area under the PD variable-time effect curve from time 0 to Week X
BMI	Body mass index
BSA	body surface area
CI	confidence interval
C max	maximum concentration
CMH	Cochran-Mantel-Haenszel
CR	complete response
CSR	clinical study report
CT	computerized/computed tomography
CTCAE	Common Terminology Criteria for Adverse Events
C trough	trough concentration
CV	Coefficient of Variation
DSMB	Data Safety Monitoring Board
ECG	electrocardiogram
ECOG	Eastern Cooperative Oncology Group
eCRF	electronic case report form
ENR	Enrolled Set
EOS	End of Study

---

Document:

Author:

Version Number:

Version Date:

Final v1.0

10Sep2019

Template No: CS\_TP\_BS016 Revision 4

Reference: CS\_WI\_BS005

Effective Date: 01Apr2016

FAS	Full Analysis Set
FL	follicular lymphoma
FLIPI-2	Follicular lymphoma international prognostic index 2
IUDR	Imputation Using Drop-out Reason
i.v.	intravenous(ly)
IWG	International Working Group
LTBFL	low tumor burden follicular lymphoma
MAR	missing at random
MedDRA	Medical Dictionary for Regulatory Activities
MI	Multiple Imputation
MRI	Magnetic Resonance Imaging
NCI	National Cancer Institute
NED	No evidence of disease
NRI	non-responder imputation
ORR	overall response rate
PD	pharmacodynamic(s)
PD	progressive disease
PDS	Pharmacodynamic Analysis Set
PET	positron emission tomography
PK	pharmacokinetic(s)
PKS	Pharmacokinetic Analysis Set
PML	progressive multifocal leukoencephalopathy
PP	Per-protocol
PR	partial response
PT	Preferred Term
RAN	Randomized Set
RAUC 0-168	accumulation ratio for AUC 0-168
RC max	accumulation ratio for C max
RDI	Relative dose intensity
SAE	serious adverse event
SAF	Safety Analysis Set
SAP	Statistical Analysis Plan

---

Document:

Author:

Version Number:

Version Date:

Final v1.0

10Sep2019

Template No: CS\_TP\_BS016 Revision 4

Effective Date: 01Apr2016

Reference: CS\_WI\_BS005

SD	stable disease
SEM	Standard error of the mean
SOC	System Organ Class
TEAE	treatment-emergent AE
TTE	time to event
ULN	upper limit of normal
US	United States
User ID	user identification
WHO-DD	World Health Organization-Drug Dictionary

---

Document:

Author:

Version Number:

Final v1.0

Version Date:

10Sep2019

Template No: CS\_TP\_BS016 Revision 4

Reference: CS\_WI\_BS005

Effective Date: 01Apr2016

## 1. Introduction

This document describes the rules and conventions to be used in the presentation and analysis of pharmacokinetics (PK), efficacy, safety, pharmacodynamics (PD), and immunogenicity data for Protocol AGB002. It describes the data to be summarized and analyzed, including specifics of the statistical analyses to be performed. The following analyses will be performed for this study: data and safety monitoring board (DSMB) analyses, analysis for Week 12, for inclusion in week 28 clinical study report (CSR), analysis for Week 28 (Week 28 CSR) and Week 52 (Week 52 CSR) which is an addendum of Week 28 CSR.

This statistical analysis plan (SAP) is based on protocol version amendment 03, dated 03Nov2017.

## 2. Study Design and Study Objective

### 2.1. STUDY OBJECTIVE

#### 2.1.1. PRIMARY OBJECTIVE

The primary objective of the study is to compare the efficacy of SAIT101 with rituximab licensed in the European Union (hereafter designated MabThera®) when administered as a first-line immunotherapy in patients with low tumor burden follicular lymphoma (LTBFL).

#### 2.1.2. SECONDARY OBJECTIVE

The secondary objectives of the study are to evaluate SAIT101 versus MabThera® with respect to:

- Safety and tolerability;
- Immunogenicity;
- Pharmacokinetics (PK) and pharmacodynamics (PD) in the PK/PD sub-population of patients.

---

Document:

Author:

Version Number:

Version Date:

Final v1.0

10Sep2019

Template No: CS\_TP\_BS016 Revision 4

Effective Date: 01Apr2016

Reference: CS\_WI\_BS005

## 2.2. STUDY DESIGN

This is a multi-center, randomized, double-blind, parallel-group study to evaluate the efficacy, safety, and immunogenicity of SAIT101 versus MabThera® in asymptomatic patients with low tumor burden follicular lymphoma. This study will take place globally across approximately 165 study sites in order to randomize approximately 308 patients.

Eligible patients will be randomized to receive either SAIT101 or MabThera® monotherapy as an i.v. infusion once a week for 4 weeks. Randomization will be stratified by inclusion in the PK/PD sub-population and follicular lymphoma international prognostic index 2 (FLIPI-2) score. Patients will be followed up for up to 52 weeks from the start of the first infusion. Efficacy will be assessed at Weeks 12 and 28.

Patients who discontinue the study drug early for any reason will be required to have efficacy assessments at Week 28, and an early treatment discontinuation visit. If new treatment targeting follicular lymphoma (FL) (other than the protocol-defined scheduled treatment with rituximab monotherapy) must be started before the Week 28 assessments, then an early treatment discontinuation visit, including a computerized/ computed tomography (CT) scan, should be performed before the start of the new treatment. Patient who discontinue the study treatment will be followed-up until Week 52 (End of study - EOS) for safety and immunogenicity. For patients who need to be withdrawn from the study early, it is highly recommended that efficacy assessments are conducted at Week 28 or an early EOS visit before they are formally withdrawn. Once a patient is withdrawn from the study, no further assessments can be conducted.

A summary of the study design is shown in Figure 1.

**Figure 1.** Study Design from Protocol

---

Document:

Author:

Version Number:

Version Date:

[figure not shown]
Final v1.0

10Sep2019

Template No: CS\_TP\_BS016 Revision 4

Effective Date: 01Apr2016

Reference: CS\_WI\_BS005

### 2.3. SAMPLE SIZE CALCULATION

Response rate of MabThera® 4 weekly dosing in low tumor burden follicular lymphoma was assessed in Ardeschna et al. 2014, Kahl et al. 2014 and Colombat et al. based on systematic literature search. The Ardeschna study was the only randomized trial which compared the treatment of MabThera® alone with the ‘watch & wait’ (W&W). The month 7 response rate on MabThera® monotherapy was estimated to be 77% with 95% confidence interval (CI) (66%-85%), considering the lower bound of 95% CI of response rate to be 66%, the highest non-response rate of MabThera® is estimated as 34%. Assuming the rate of non-responders with SAIT101 will not exceed 1.5 times over the expected highest non-response rate with MabThera® at 34%, the equivalence can be declared if the non-response rate in the SAIT101 arm is less than 51%. In other words, with the lower bound of 95% CI of responder rate of MabThera® at 66%, equivalence can be declared if the response rate in the SAIT101 arm is more than 49%. As above, the estimated margin should be set less than ±17.0%.

In the reference study, the month 7 response rate in MabThera® monotherapy was estimated to be 77% with 95% CI (66%-85%) and response rate of W&W group was estimated to be 6%, giving an estimated difference in overall response rate (ORR) of 71% with 95% CI (59%-79%). The equivalence margin of ±16.0% ( $0.59 \times [1-0.73] = 0.1593$ ) was calculated to preserve at least 73% of the treatment benefit of MabThera® based on the lower bound of 95% CI of the difference in ORR.

Document:

Author:

Version Number:

Version Date:

Final v1.0

10Sep2019

Template No: CS\_TP\_BS016 Revision 4

Effective Date: 01Apr2016

Reference: CS\_WI\_BS005

To achieve 83% power with a 16.0% margin and a 77% expected ORR with 2 one-sided tests at the significance level of 0.025. nQuery Advisor 4.0 calculated the following with the given assumption: With 154 patients in each group, the observed 2-sided 95.0% CI will be expected to lie between -0.160 and 0.160 with 83% power when the Standard proportion,  $P_s$ , is 0.770 and the Test expected proportion,  $P_t$ , is 0.770; results are based on 1,000 simulations using the Newcombe-Wilson score method to construct the CI.

Thus, 154 patients in each group are able to satisfy the primary analysis of ORR, given an 83% probability of declaring equivalence in the full analysis set (FAS). Patients who discontinue the study drug early for any reason will be required to have efficacy assessments at Week 28. Allowing for a 4% drop-out rate and patients with major protocol deviations as seen in the Ardeschna et al, 147 patients in each group will give 80% probability of demonstrating equivalence in the PPS.

At least 154 patients per arm (308 patients overall) should be randomized into the study. With 154 patients, the estimated ORR with 95% CI of SAIT101 is 77% (70%-84%). ORR with 95% CI of MabThera® based on a random effect meta-analysis that include Ardeschna et al. 2014, Kahl et al. 2014 and Colombat et al. 2001 was estimated as 72% (68%-76%). The maximum difference in the upper and lower 95% CI of ORRs is  $\pm 15.0\%$ , which is smaller than the margin  $\pm 16.0\%$ , and this estimated ORR with 95% CI for SAIT101 is considered to exclude a clinically relevant. difference versus MabThera.

#### **Pharmacokinetic/ Pharmacodynamic sub-population**

For PK, assuming a coefficient of variation (CV) of 38% in both  $AUC_{0-168}$ , based on Regazzi et al. 2005 and assuming no true difference between SAIT101 and MabThera® in this parameter, 60 evaluable patients per arm are required to yield 81% overall power for comparison of  $AUC_{0-168, 1}$  and  $AUC_{0-168, 4}$  between the test and comparator treatments, using the standard two one-sided testing procedures, a 5% significance level for each one-sided test (90% CI). To ensure 120 evaluable patients are available, a total of 134 patients will be randomized for the PK/PD sub-population.

## **2.4. RANDOMIZATION**

Patients who meet the eligibility criteria will be randomized in blocks to double-blind treatment. Patients will be randomly assigned in a blinded fashion to either SAIT101 or MabThera® with a 1:1 allocation ratio. The block size(s) of the randomization will be documented in the Week 28 CSR.

---

Document:

Author:

Version Number:

Version Date:

Final v1.0

10Sep2019

Template No: CS\_TP\_BS016 Revision 4

Effective Date: 01Apr2016

Reference: CS\_WI\_BS005

## 2.5. SCHEDULE OF EVENTS

The schedule of events is provided in Table 1 in the protocol.

## 2.6. CHANGES TO ANALYSIS FROM PROTOCOL

The following updates were made:

- The PK and PD analysis sets were updated to include subjects that received at least one dose of the study drug. The PD analysis set were updated to only include subjects that have at least one measured PD variable (CD19+ B-cell count). IgM and IgG were removed from the definition of the PDS since those PD variables are measured in all subjects in the safety analysis set.
- The following criteria was not considered for the exclusion of patients from the Per Protocol Set (PPS):
  - Patient did not have available response assessment at Week 28

## 3. Planned Analyses

The following analyses will be performed for this study:

### 3.1. DATA AND SAFETY MONITORING BOARD (DSMB)

It is anticipated, there will be at least 4 DSMB meetings for reviewing safety data in this study, with timing of review meetings based on first 24 patients, 50% of patients at Week 4, all patients at Week 24 and Week 36. Analysis for DSMB meetings will be described in a separate DSMB SAP. The fourth DSMB is optional and will be confirmed if needed after the third DSMB. For additional details on DSMB meetings, please refer to the DSMB charter dated 07Oct2016.

### 3.2. FINAL ANALYSIS

The study will be unblinded at Week 28 for the primary endpoint analysis and a CSR will be prepared based on data up-to and including Week 28 for all patients. The investigators and patients will remain blinded to treatment assignment during the post Week 28 follow up period.

---

Document:

Author:

Version Number:

Version Date:

Final v1.0

10Sep2019

Template No: CS\_TP\_BS016 Revision 4

Effective Date: 01Apr2016

Reference: CS\_WI\_BS005

After the last patient has completed Week 52 of the study, a CSR addendum (Week 52 CSR) will be prepared to report the additional safety, PK, and PD data .

### **3.3. EXPLORATORY ANALYSIS**

Additional exploratory subgroup analyses, i.e., in addition to the analyses described in this SAP, may be performed as ad hoc analyses as deemed necessary. The subgroups to be used for this analysis may be based on, but not limited to, the results of analysis of PK, PD, efficacy, safety, immunogenicity and concomitant medication.

## **4. Analysis Sets and Protocol Deviations**

Analysis sets or exclusions therein will be determined through review of clinical database and protocol deviations prior to database lock and the unblinding of the study. A blinded data review meeting will be set up then to decide on the final allocation rules to assign patients to the analysis sets. Agreement and sponsor authorization of patient inclusion in/exclusion from each Analysis Set will be obtained prior to the unblinding of the study for final analysis.

Analysis sets will be listed by patient.

### **4.1. ENROLLED SET [ENR]**

The Enrolled Set (ENR) consists of all patients who provided informed consent for this study.

### **4.2. RANDOMIZED SET [RAN]**

The Randomized Set (RAN) consists of all screened patients who received a randomization number. For analyses and displays based on RAN, patients will be classified according to the treatment they were assigned at randomization.

### **4.3. FULL ANALYSIS SET [FAS]**

The Full Analysis Set (FAS) consists of all RAN patients in accordance with the intended treatment arm, regardless of the treatment actually received. However, patients who do not qualify for randomization and are inadvertently randomized into the study will be excluded from the FAS, provided these patients do not receive study drug. The FAS will

---

Document:

Author:

Version Number:

Version Date:

Final v1.0

10Sep2019

Template No: CS\_TP\_BS016 Revision 4

Effective Date: 01Apr2016

Reference: CS\_WI\_BS005

be considered as the primary analysis sets for the primary efficacy endpoint and one of the analysis sets for other efficacy endpoints.

The Full Analysis Set for exploratory analysis (FASEXP) consists of all FAS patients who had their tumor assessment measured by positron emission tomography computerized tomography (PET-CT) scan.

#### **4.4. SAFETY ANALYSIS SET [SAF]**

The Safety Analysis Set (SAF) consists of all RAN patients who received at least one dose of study drug. Patients will be analyzed according to the treatment received. SAF is used as the basis for all safety analyses.

If there is any doubt whether a patient was treated or not, they will be assumed treated for the purposes of analysis.

#### **4.5. PER PROTOCOL SET [PPS]**

The Per Protocol set (PPS) consists of all FAS patients who have the diagnosis of FL confirmed by central pathology review and have no major protocol deviations that would significantly impact the study outcome, as determined by blinded medical review. A patient may be excluded from the PPS for, but not limited to, any of the following conditions.

- Patient did not meet inclusion/exclusion criteria
- Infusion of wrong study drug occurred
- Patient did not receive all 4 infusions of study drug (Days 1, 8, 15, and 22)
- Intake of prohibited treatment, this is subject to evaluation of the clinical relevance of the treatment intake

Major protocol deviations and/or the situation that lead to exclusion from the PPS will be specified and authorized prior to unblinding the treatment arms. Efficacy endpoints will also be summarized on the PPS.

The Per Protocol set for exploratory analysis (PPSEXP) consists of all the PPS patients who had their tumor measured by positron emission tomography computerized tomography (PET-CT) scan.

---

Document:

Author:

Version Number:

Version Date:

Final v1.0

10Sep2019

Template No: CS\_TP\_BS016 Revision 4

Effective Date: 01Apr2016

Reference: CS\_WI\_BS005

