4.11 Allowed and Prohibited Treatments

Medication that is considered necessary for the patient's safety (e.g., as a result of an AE) may be given at the Investigator's discretion.

All concomitant medications, whether allowed or not, must be recorded on the eCRF.

Use of prohibited treatment is a protocol violation.

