4.11.2 Prohibited Treatments

Treatment with any other experimental drug or a concomitant chemotherapy, anticancer hormonal therapy, radiotherapy, or immunotherapy is prohibited during study participation. This includes additional doses of rituximab or SAIT101 after the initial 4-weekly doses.

If a patient requires tumor targeting treatment for FL other than the protocol-defined treatment with rituximab or SAIT101 monotherapy due to disease progression based on tumor assessments done at investigational site, he or she will be considered as a treatment failure and should be discontinued from the study treatment. (See Section 3.3.1.2) Patients with progressive disease should be treated with an adequate therapy according to judgment of the treating physician. In such case, patient will be followed-up until Week 52 (EOS) for safety and immunogenicity.

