8.5.1 Analysis Populations

The following analysis sets are defined for this study:

Randomized Set (RAN)

The Randomized Set (RAN) will consist of all patients who receive a randomization number.

Full Analysis Set (FAS)

The Full Analysis Set (FAS) will consist of all randomized patients in accordance with the intended treatment arm, regardless of the treatment actually received.

Safety Analysis Set (SAF)

The Safety Analysis Set (SAF) will consist of all randomized patients who received at least one dose of study drug. The SAF will be used as the basis for all safety analyses.

Per-protocol Set (PP set)

The PP set is defined as FAS patients who have the diagnosis of FL confirmed by central pathology review and have no major protocol deviations that would significantly impact the study outcome, as determined by blinded medical review. A patient may be excluded from the PP set for, but not limited to, any of the following conditions:

- Patient did not meet inclusion/exclusion criteria
- Infusion of wrong study drug occurred
- Patient did not receive all 4 infusions of study drug (Days 1, 8, 15, and 22)
- Intake of prohibited treatment, subject to evaluation of clinical relevance of the intake
- Patient did not have available response assessment at Week 28

All decisions to exclude patients from PP set will be made prior to database release.

The efficacy analyses will be applied for both the PP set and FAS and FAS will be considered as primary efficacy analysis population.

Pharmacokinetic Analysis Set (PKS)

The PKS will include all patients who receive the planned dose of study drug, have at least one measured drug serum concentration at a scheduled time point post-dose, and have no major protocol deviations or violations thought to significantly affect the PK of the drug.

Pharmacodynamic Analysis Set (PDS)

The PDS will include all patients who receive the planned dose of study drug, have at least one measured PD variables (CD19+ B cell count, IgG, and IgM) at a scheduled time point post-dose, and have no major protocol deviations or violations thought to significantly affect the PD of the drug.

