8.8 Efficacy Analyses

The statistical analysis of the primary endpoint for this study will be performed after the last patient has completed the Week 28 response assessment. All efficacy data will be analyzed at this time, plus all PK, PD, immunogenicity, and safety data available at the time of data

cut-off, and these data will be reported in the CSR (Week 28 CSR). After the last patient has completed Week 52 of the study, a CSR addendum (Week 52 CSR) will be prepared to report the additional safety data.

Efficacy will be assessed centrally as CR, PR, SD, and PD, as defined in IWG criteria 2007, and TTE. The main efficacy endpoint will be the difference in ORR (CR+PR) at Week 28, approximately 24 weeks after the completion of study treatment. The efficacy analyses will be applied for both the PP set and FAS. FAS will be considered as primary efficacy analysis population and analysis in PP set will be conducted as a sensitivity analysis.

In FAS, patients without a response assessment at Week 28 will be handled using a conservative approach by imputation using drop-out reason (IUDR), where Non-responder imputation (NRI) method in case of treatment related reasons and otherwise multiple imputation (MI) procedure assuming missing at random (MAR) will be applied. For the PP set, all available data will be used for analysis.

Potential withdrawal reasons are considered as follows based on previous studies; The major reason of missing response assessment at Week 28 is assumed to be either the start of new treatment of FL due to lack of efficacy or toxicity based on Ardeshtna et al. In such reasons related to treatment (i.e. treatment failure requiring tumor targeting treatment for FL other than the protocol-defined treatment, death due to progressive disease), patients without a response assessment at Week 28 will be handled as non-responders. Missing responses unrelated to treatment (i.e. withdrawal by subject, pregnancy) as seen in the Colombat et al. would be considered ignorable missing at random (MAR) and multiple imputation procedure using logistic regression method will be used to impute the missing response assessment at Week 28 (responder versus non-responder). No imputation will be applied when the reasons are unknown whether they are related to treatment or not (i.e. lost to follow-up).

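### New lymphoma treatment given after treatment failure is classed as prohibited treatment, so the per-protocol set may lose treatment failures and its three sensitivity analyses lean toward equivalence

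*SAP*

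**What the plan says.** Protocol 4.11.2 names other experimental drugs, chemotherapy, anticancer "hormonal therapy, radiotherapy, or immunotherapy is prohibited during study participation". It gives no exception after progression. The same section deals with a patient who needs other FL treatment because of progression: "he or she will be considered as a treatment failure and should be discontinued from the study treatment". It then adds: "Patients with progressive disease should be treated with an adequate therapy according to judgment of the treating physician".

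Protocol 4.11 states without qualification: "Use of prohibited treatment is a protocol violation".

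Both definitions of the per-protocol set carry this forward. Protocol 8.5.1 lists "Intake of prohibited treatment, subject to evaluation of clinical relevance of the intake", and SAP 4.5 lists "Intake of prohibited treatment, this is subject to evaluation of the clinical relevance of the treatment intake". In the SAP the list is introduced by "A patient may be excluded from the PPS for, but not limited to, any of the following conditions", and the decision belongs to a blinded medical review.

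On missing data, Protocol 8.8 says: "For the PP set, all available data will be used for analysis". SAP Table 1 marks imputation as not applicable in the three PPS rows (1-2, 2-2 and 5-2).

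**The concern.** A patient managed as Protocol 4.11.2 directs acquires a listed ground for leaving the PPS. That ground is a consequence of the randomised treatment having failed, so exclusion would depend on the outcome.

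The plan treats the same event differently elsewhere. For the primary endpoint, SAP 16.1.1 reads response only until the new therapy starts, and SAP 16.1.2 counts patients without a Week 28 assessment after such therapy as non-responders. For time to event, SAP 16.2.1 counts the start of new FL treatment as an event. Only in the PPS can it become a deviation.

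In an equivalence trial the direction matters. Removing non-responders raises the response rate in both arms. It raises it more in the arm with more failures, so the estimated difference moves toward zero. An analysis meant to test the robustness of the equivalence conclusion would then be tilted toward confirming it.

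**Working it through.** **1. The plan's own power.** Inputs from Protocol 8.4: overall response rate (ORR) 77% in both arms, margin ±16.0 points, two-sided 95% Newcombe-Wilson interval. Exact binomial enumeration of the unstratified interval gives 84.0% at 154 per arm (stated 83%) and 81.3% at 147 per arm (stated 80%). The stated figures are reproduced closely enough to use the same method below.

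**2. A plausible rescue rate.** The documents give no rate of new FL treatment by Week 28. Protocol 1.2.2 reports that 78% of patients on rituximab induction needed no new therapy at 3 years in the randomised comparison with watchful waiting. Assuming a constant hazard:

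- hazard = -ln(0.78)/3 = 0.0828 per year
- started by day 190: 1 - exp(-0.0828 × 190/365.25) = 4.2%
- started by 28/52 of a year: 4.4%
- started by day 204: 4.5%

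With 23% non-responders, 4.4/23 is about 19% of non-responders.

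**3. Effect of exclusion.** Let p be an arm's true ORR and r the share of its patients who are rescued and excluded, all assumed to be non-responders. Then PPS ORR = p/(1 - r). If a share f of non-responders is rescued, r = f(1 - p).

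Take 154 per arm, MabThera 77% and SAIT101 61%, so the true difference lies on the margin. The chance of declaring equivalence is exact in the first row and simulated in the others.

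| Rescued and excluded (SAIT101 / MabThera) | PPS ORR (SAIT101 / MabThera) | Difference | Chance of declaring equivalence |
|---|---|---|---|
| none | 61.0% / 77.0% | -16.0 | 2.7% |
| 19% of non-responders each (7.4% / 4.4% of patients) | 65.9% / 80.5% | -14.6 | 4.8% |
| 10% / 4.4% of patients | 67.8% / 80.5% | -12.8 | 9.5% |
| 50% of non-responders each (19.5% / 11.5% of patients) | 75.8% / 87.0% | -11.2 | 17% |
| 20% / 4% of patients | 76.3% / 80.2% | -4.0 | 64% |

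For example, row 2: 0.61/(1 - 0.19 × 0.39) = 0.659 and 0.77/(1 - 0.19 × 0.23) = 0.805.

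With a true difference of -10 points (67% against 77%) and f = 19%, the PPS difference is -9.0 points and the chance of declaring equivalence rises from 22.7% to 29.4%. With no true difference, PPS power rises from 84% to 87%.

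**4. The PPS allowance.** Protocol 8.4 allows 4% for drop-out and major deviations together (154 to 147 per arm). Rescue of 4.2% to 4.5%, if excluded, would use that allowance by itself.

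Limits: the calculation is unstratified, assumes a constant hazard and treats every rescued patient as a non-responder. SAP 16.1.1 refers to best response, so a Week 12 responder who later progresses might count as a responder. That would make the effect smaller.

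**The case against.** The strongest reply is that the plan leaves the matter to judgement and does not rest its conclusion on the PPS. Much of this stands.

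- A reader might infer that the rules remove every rescued patient. They do not. Exclusion is permitted, case by case, after an evaluation of clinical relevance and a blinded review. The treatment-failure label in Protocol 4.11.2 gives that review a reason to keep such patients.
- A reader might infer that a real difference would be hidden from the trial's conclusion. The equivalence decision is made on the FAS, which keeps these patients (SAP 16.1.1 to 16.1.3). Five of the eight sensitivity analyses in SAP Table 1 also use the FAS, one with full non-responder imputation.
- A reader might infer that a rescued patient who is kept would drop out anyway for want of a Week 28 scan. The documents do not establish this. Protocol 3.3.1.2 calls for a CT before new treatment, SAP 5.3 maps early-discontinuation data to the next visit when that visit is missing, and SAP 2.6 removes the missing-Week-28 exclusion. What remains is an ambiguity for a PPS patient with no reading at all.
- A reader might take the last table row as the expected size. No passage supports 20% against 4%. Under the same constant-hazard assumption, the 46% free of new therapy at 3 years under watchful waiting implies only about 12.6% to 13.5% treated by day 190 to 204. That row has SAIT101 patients rescued more often than untreated patients.

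The reply does not remove the gap. No criterion tells the review how to separate rescue after failure from contamination, and anti-lymphoma therapy is easily judged relevant to response. Blinding to arm does not protect against exclusion that depends on outcome.

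**Conclusion.** The point holds as a defect in the PPS definition. As written, the plan allows treatment failures to be removed from sensitivity analyses 1-2, 2-2 and 5-2 because they received the therapy the protocol directs, and the resulting bias favours equivalence. The FAS primary analysis is unaffected.

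At the rescue rate implied by the one relevant figure in the documents, the PPS difference shrinks by about 1.4 points at the margin and false equivalence rises from about 2.7% to 4.8%. With moderately unequal rescue it reaches about 9.5%. Much larger effects need strongly unequal rescue, or rescue far more common than that figure suggests. All these sizes assume that every rescued patient is a non-responder and that the review excludes every one of them. They are therefore upper figures for each rescue rate.

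**What to change.** Before unblinding:

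1. In Protocol 8.5.1 and SAP 4.5, reword the exclusion ground to *prohibited treatment other than new FL treatment started after treatment failure*.
2. State that these patients stay in the PPS and that their response is derived as in the FAS under SAP 16.1.1 and 16.1.2: read until the new therapy starts, and non-responder if there is no assessment. A blanket rule making all of them non-responders would give the PPS a different endpoint from the primary analysis.
3. Reconcile Protocol 4.11 with 4.11.2 on whether treatment given under 4.11.2 is a violation. This concerns how the event is classified and leaves patient care unchanged.

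The cost is wording in two documents and one programming rule. Sample size and the primary analysis do not change. The PPS response rate will be slightly lower than if failures were removed, and so will PPS power: in the illustration with no true difference, 84% with these patients kept against 87% with them excluded.
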